7.5 Confidentiality

All local legal requirements regarding data protection will be enforced. All study findings and documents will be regarded as confidential. The Investigator and members of his/her research team must not disclose such information without prior written approval from Sensei. The anonymity of participating patients must be maintained. Throughout documentation and evaluation, the patients will be identified on CRFs and other documents submitted to Sensei

by their initials, birth date, and their patient number. Documents that are not to be submitted to Sensei, and that identify the patient (e.g., the signed ICF), must be maintained in confidence by the Investigator. The patients will be told that all study findings will be stored and handled in strictest confidence, according to local requirements. Patients will be informed that authorized research Investigators and agents of the FDA, other recognized regulatory authorities, and authorized representatives of the Sponsor, Sensei, have the right to inspect their medical records.

8. Investigators and Study Administrative Structure

This is a Phase 1 trial involving study centers located in the United States. The Investigator(s) responsible for the conduct of the study at their site, in compliance with this Protocol, are identified on the *Signature of Agreement Page* (Appendix B).

8.2 Data Handling and Recordkeeping

8.2.1 Electronic Case Report Form (eCRF)

Electronic case report forms will be provided via a Part 11 compliant database; patients will not be identified by name on any study documents. Each patient shall be identified by the patient identifying number that will be assigned by the Sponsor.

8.2.2 Maintenance of Study Records

The Investigator must retain a copy of all study documents, including reports to the IRB, regulatory authorities, and Sensei in accordance with FDA regulations.

The Investigator must maintain study documents:

- for a minimum of two years following the date the marketing application (NDA/BLA) is approved for the indication for which the drug was investigated; or,
- for a minimum of two years following the release date of the final report, if no marketing application is to be filed by Sensei, or if the marketing application is not approved for the indication for which the drug was investigated or is discontinued and the FDA has been notified; or,
- for a minimum of 15 years after the completion or discontinuation of the study to be filed in support of the registration in the European Union.

If the Investigator relocates, retires for any reason, or withdraws from the study, the study records may be transferred to an acceptable designee, such as another Investigator, another institution, or to Sensei. The Investigator must obtain Sensei's written permission before disposing of or transferring any records.

8.3 Final Report

Upon terminating the study, the Investigator will submit a final report to the IRB in keeping with local IRB regulations. This report should include any deviations from the protocol, the number and types of patients evaluated, the number of patients who discontinued, including reasons, results of the study, AEs, and a conclusion summarizing the results.

If requested by the Investigator, at the completion of the study and following analysis of the data, Sensei will supply a tabulated listing of data and a final clinical statistical report. A copy of the final study report and corrected CRFs, including a receipt to be returned to the Sensei Clinical Monitor, will be provided to each Investigator following its release by Sensei.

8.4 Publication and Use of Study Findings

By signing the study protocol, the Investigator agrees with the use of results of the study for the purposes of national and international registration, publication, and information for medical and pharmaceutical professionals. If necessary, the authorities will be notified of the Investigator's name, address, qualifications, and extent of involvement. Sensei will prepare an *Integrated Clinical/Statistical Report*. Any publication/presentation of data must include the entire study population. Submission of data for publication/presentation will be coordinated and approved by Sensei in collaboration with the Investigator. Sensei will determine authorship of any publication by enrollment in consultation with the principal Investigator.

10. LIST OF APPENDICES

| Appendix | Title | |
|-----------------|---|--|
| А | Eastern Cooperative Oncology Group Performance Status (ECOG) | |
| В | Principal Investigator Signature of Agreement Page | |

APPENDIX A: ECOG PERFORMANCE STATUS

| ECOG PERI | ECOG PERFORMANCE STATUS* | | |
|-----------|---|--|--|
| GRADE | ECOG | | |
| 0 | Fully active, able to carry on all pre-disease performance without restriction | | |
| 1 | Restricted in physically strenuous activity but ambulatory and able to carry out work of a light or sedentary nature, e.g., light house work, office work | | |
| 2 | Ambulatory and capable of all self-care but unable to carry out any work activities. Up and about more than 50% of waking hours | | |
| 3 | Capable of only limited self-care, confined to bed or chair more than 50% of waking hours | | |
| 4 | Completely disabled. Cannot carry on any self-care. Totally confined to bed or chair | | |
| 5 | Dead | | |

*As published in: *Am. J. Clin. Oncol.*: Oken, M.M., Creech, R.H., Tormey, D.C., Horton, J., Davis, T.E., McFadden, E.T., Carbone, P.P.: Toxicity And Response Criteria Of The Eastern Cooperative Oncology Group. *Am J Clin Oncol* 5:649-655, 1982.

10.2 Mock Tables, Figures, and Listings

27

1 List of Abbreviations and Definition of Terms

Only abbreviations and terms relevant to the SAP are repeated herein. The reader is referred to the protocol for the complete and comprehensive list of abbreviations and definitions of terms for the study.

Abbreviation/Term	Definition
ADaM	Analysis data Model
AE	Adverse Event
ATC	Anatomical Therapeutic Chemical
BMI	Body Mass Index
CBC	Complete Blood Count
CDISC	Clinical Data Interchange Standards Consortium
CH50	Total Complement Activity
CTL	Cytotoxic CD8+ T-lymphocytes
DLT	Dose-limiting Toxicity
ECG	Electrocardiogram
ECOG	Eastern Cooperative Oncology Group
eCRF	Electronic Care Report Form
EDC	Electronic Data Capture
НААН	Human aspartyl-asparaginyl-β-hydroxylase
MedDRA	Medical Dictionary for Regulatory Activities
MTD	Maximum Tolerated Dose
NCI-CTCAE	National Cancer Institute Common Terminology Criteria for Adverse Events
SNS-301	HAAH bacteriophage lambda constructs: HAAH-1 λ
PBMC	Peripheral Blood Mononuclear Cells
PD	Pharmacodynamic
PSA	Prostate-specific Antigen
РТ	Preferred Term
RP2D	Recommended Phase 2 Dose
SAE	Serious Adverse Event
SAP	Statistical Analysis Plan
SD or sd	Standard Deviation
SDTM	Study Data Tabulation Model
SOC	System Organ Class
TEAE	Treatment Emergent Adverse Event
WHO	World Health Organization

2 Introduction

This document presents a statistical analysis plan (SAP) for Sensei Biotherapeutics, Inc. Protocol SNS0216, Phase I, Open-Label Trial to Evaluate the Safety and Immunogenicity of SNS-301 in Cancer Patients.

Reference materials for this statistical plan include the Protocol SNS0216 Version 5.0 (dated 12 June 2018) and Electronic Case Report Forms (eCRF) (dated 07 August 2018).

3 Study Objectives

Primary:

To determine the maximum tolerated dose (MTD) of SNS-301 based on the incidence of dose-limiting toxicities (DLT) and the maximum administered dose of SNS-301, when administered every 21 days in patients with biochemically relapsed prostate cancer.

Secondary:

To assess the overall safety, immunogenicity and clinical activity of SNS-301.

4 Study Design

As background for the statistical methods presented below, this section provides an overview of the study design. This overview is a summary only. The protocol is the definitive reference for all matters discussed in what follows.

This is a Phase I, open-label study of SNS-301, an HAAH (Human aspartyl-asparaginyl- β -hydroxylase)-directed nanoparticle vaccine, given intradermally in cohorts of patients with biochemically relapse prostate cancer, using a fixed dose-escalation schema every 21 days to establish the MTD.

Following informed consent and screening, patient serum will be tested for the expression of HAAH. Patients who test positive for HAAH expression in fresh serum may be continued in the study. Baseline biochemical testing (chemistry, complete blood count [CBC], coagulation panel, total complement activity [CH50], and prostate-specific antigen [PSA]) will be obtained prior to study treatment administration.

Figure 4-1. DOSE-ESCALATION STUDY DESIGN (3+3 SCHEMA)

Treatment will consist of single repeated doses of SNS-301 administered every 21 days. A traditional 3+3 dose-escalation schema will be used to determine the MTD of SNS-301 for the first 2 doses and a modified dose-escalation schema with 6 patients per dose level for the remaining dose (Figure 4-1). Planned doses of SNS-301 are 2.0 x 10^{10} , 1.0×10^{11} and

 3.0×10^{11} particles per administration diluted to 1 mL and administered intradermally. Additional patients will be enrolled at the highest dose level until at least 6 patients can be evaluated even if no DLTs are observed at the dose. Planned treatment may continue for two additional doses of SNS-301 administered every 21 days. Serum and whole blood samples will be obtained on the day of study treatment administration (Day 1) and 21 days thereafter. In patients who continue to receive study treatment, biochemical and immunologic testing will continue every 21 days.

The MTD will be determined over the first 21-day interval following a single dose of SNS-301 in 3 consecutive dose cohorts. The MTD will be considered the dose level lower than that dose which produces \geq 2 DLTs in 3 or 6 patients. A DLT will be considered a protocolspecified drug related grade 3-4 (National Cancer Institute Common Terminology Criteria for Adverse Events [NCI-CTCAE] V 4.03) adverse experience). The recommended Phase 2 dose (RP2D) will be the highest dose administered if no MTD is observed.

Dose cohorts will be enrolled sequentially.

Dose-escalation will proceed once all patients in a cohort (unless the MTD is observed) have completed a 21-day safety evaluation following the first dose of study treatment in the cohort. Planned treatment may continue for an additional 2 extra doses of SNS-301 administered every 21 days. Additional patients will be enrolled at the highest dose level until at least 6 patients can be evaluated even if no DLTs are observed at the dose. In patients who tolerate SNS-301, additional treatment may be continued with single doses of SNS-301 at their current dose level to maintain geometric mean titer (GMT) of HAAH antibodies to no less than 4 times the baseline value for at least six months (9 injections). Treatment will be terminated with the 9th injection or will otherwise be terminated at any time upon the observance of PSA doubling < 90 days or occurrence of unacceptable toxicity as determined by the Investigator (either for that patient or in their dose cohort). After termination, patients will be followed for an additional 6 months with monthly PSA levels and imaging studies as needed.

Once the MTD/RP2D is determined, patients receiving ongoing treatment may be escalated to that dose for subsequent treatments and receive a maximum of 9 injections. Patients who have received more than 9 injections due to the timing of the amendment limiting therapy to 6 months (9 doses), will be stopped at their last dose received and be followed for 6 months as with other patients. These subjects will continue to be followed for safety and biochemical PSA monitoring on a monthly basis for 6 months and are eligible to resume SNS-301 in case of increases in PSA doubling to < 90 days or other evidence of disease progression and decline in immunological parameters.

Exploratory pharmacodynamic (PD) analysis will be performed using dose, vaccinespecific antibody response (geometric mean titer), antigen-specific T and B cell indices, and the relative expression of HAAH in each patient's tumor. The PD will be balanced and optimized to the degree of antigen-specific immune response and minimized for the production of regulatory immune processes. Safety endpoints will be evaluated by the incidence and severity of administration site reactions, changes in biochemical safety measures, general incidence and types of AEs, serious adverse events (SAEs), and other overt toxicities.

The duration of the study for each patient will include an up to 8-week screening phase, 21day study treatment cycles for 9 cycles and 6 months of follow up including monthly PSAs, and an end of study visit (28 days post last dose of study treatment). Patients may continue to receive single repeated doses of SNS-301 at their original dose level (or at the MTD when it is determined) every 21 days or until the observance of PSA doubling < 90 days or unacceptable toxicity (either for that patient or in their dose cohort).

A complete schedule of procedures and assessments is in Table 4-1.

Assessment	Screen (D-56+7 ^e to D0)	A	Cycle		Cycl	le 2-3	Additional Treatments	Follow- up/End of study
	/	D1	D8 ± 2	D15±2	D22 ± 3	D43 ± 3	Every 21 ± 3 day	Every 28 ± 3 days after final treatment for 6 Months
Signed Informed Consent	X							
HAAH assessment ^a	X				_			
Demographics	Х					•		
Medical/Oncology History	Х							
Tumor Burden Evaluation ^d	Х							
Baseline Signs and Symptoms	Х							
Physical Examination	Х							Х
Symptom-Directed		Х	Х	Х	Х	Х	Х	
Physical Examination		• /\	N .	\wedge				\wedge 1
Vital Signs	X	X	X	X	Х	X	X	/ X
ECOG Performance Score	Х	Х	Х	Х	Х	Х	Х	Х
ECG	Х	Х			Х	Х	Х	Х
PSA	Х	Х			Х	Х	Х	Х
Hematology ^b	Х	Х	Х	Х	Х	Х	Х	
Chemistry ^b	Х	Х	Х	Х	Х	Х	Х	
Coagulation, CH50 ^b	Х	Х	Х	Х	Х	Х	Х	
Study Treatment administration		Х			Х	X	X	
Physician Administration Site Assessment		Х	Х		Х	X	X	
Immunologic Blood Collection ^c		Х			Х	X	Х	Х
Cohort enrollment evaluation					Х			
Concomitant Medications Collection		Х	Х	Х	Х	X	Х	Х
Adverse Events Assessments ^f		Х	Х	Х	Х	X	Х	Х

- a HAAH assessment: following informed consent, archived prostate tumor tissue and patient serum will be tested for the expression of HAAH. Only patients who test positive for HAAH expression in archived tumor tissue (if available) or fresh serum may be continued in the study. HAAH assessments are not subject to the 56-day screening window and are valid for 6 months. Patients who are negative for HAAH may be followed for 6 months and if PSA rises over that period time, they can enroll in the study provided that tissue or fresh serum is positive for HAAH
- b Biochemical testing (chemistry, complete blood count, coagulation, and total complement CH50,) to be obtained within 14 days prior to study drug administration if screening period is between 3 and 8 weeks. PSA levels are also to be evaluated at screening and within 14 days prior to study drug administration if screening period is between 3 and 8 weeks.
- c Immunologic blood collection: to be taken pre-dose on the day of study drug administration (Day 1) and every 21 days thereafter. Following the 9th dose (or last dose otherwise), PSA levels and other assessments will be followed on a monthly basis for 6 months. Patients with evidence of progression and declining HAAH immune parameters will have the option of resuming therapy on the study protocol.
- d Baseline radiological tumor burden evaluation consists of a baseline pelvic MRI or CT scan in addition to bone scan. These studies will need to be performed within 56 days (+ 7 days) prior to the start of the study.
- e Patients that have a delay in screening beyond 56-days may be re-screened for randomization.
- f Adverse events that occur post patient receiving study drug. Should Adverse event occur prior to patient receiving study drug they will be captured as Medical History.

5 Analysis Populations

There will be two analysis populations defined for this study. All populations will be analyzed as treated.

- 1. The "Safety Population" will be comprised of all subjects who received a study treatment administration.
- 2. The "Immunologic Population" will be comprised of all subjects who received a study treatment administration and for whom any follow-up immunologic data were recorded for a specific immunological analysis.

6 Analysis Variables

In what follows, variables to be analyzed have been grouped under the headings 6.1 to 6.5. Additional variables may be added as further drafts of the eCRF and this SAP are developed and/or as discussion unfolds concerning the usefulness of *derived* variables formulated using the information presented below.

6.1 Study Drug Dosing

- Study treatment administered
- Treatment dose

6.2 Demographics and Baseline Characteristics

- Gender
- Age
- Race
- Ethnicity
- Weight
- Height
- Body mass index (BMI)
- Medical/oncologic history
- Prior medications

6.3 Primary Endpoints

Primary endpoints are derived at the end of each cohort and are not within the scope of the SAP.

- Determine the MTD
- Determine the RP2D if different than the MTD
- Determine the DLTs possibly-, probably-, or definitely related to SNS-301 (based on the NCI-CTCAE V4.03 criteria):
 - Grade 4 non-hematological toxicities (excluding alopecia) of any duration
 - Grade 3 non-hematologic (non-laboratory) toxicity lasting > 3 days despite optimal supportive care
 - Any Grade 3 or Grade 4 non-hematologic laboratory value if: a). Medical intervention is required to treat the subject; b), the abnormality leads to hospitalization; c). The abnormality persists for >1 week.
 - Grade 4 hematologic toxicity, other than those specified in criteria 5 and 6 below, lasting > 7 days
 - Grade 3 or Grade 4 febrile neutropenia of any duration
 - Grade 3 thrombocytopenia in combination with a grade 3 or greater blood and lymphatic system disorder

• Grade 3 AST or ALT that is associated with a grade 2 rise in bilirubin

6.4 Secondary Endpoints

- Incidence of administration site reactions
- Biochemical safety and tolerability (hematology, serum chemistry, coagulation, CH50)
- Geometric mean titers of anti-HAAH antibodies by dose
- Antigen-specific Cytotoxic CD8+ T-lymphocytes (CTL) responses by dose
- Production of B cell and T cell response of interest

Clinical Secondary Endpoints:

- Change in the prostate-specific antigen (PSA) velocity
- Reduction in the PSA doubling time from pre-baseline

Pharmacodynamic Secondary Endpoints:

- Duration of antigen-specific anti-HAAH antibody titers
- Changes in the amplitude or duration of the production of anti-HAAH antibodies
- Correlation of anti-HAAH titers and serum HAAH levels

6.5 Safety Variables

In addition to the assessments listed as endpoints above, safety assessments include the following:

- AEs and SAEs
- Vital signs (blood pressure, heart rate, body temperature)
- Eastern Cooperative Oncology Group (ECOG) performance score
- ECG (heart rate, PR interval, QRS interval, QT interval, QTcF interval, atrial rate, ventricular rate)
- Concomitant medications
- Physical examination

7 Statistical Methodology

7.1 Sample Size

Cohorts of 3 or 6 patients will be screened and treated at each dose level. The actual sample size may vary depending on the incidence of DLT during the first cycle at a given dose level.

Approximately 18 patients will be included and treated in the trial.

7.2 Randomization

Not applicable.

7.3 Interim Analysis

No interim analysis is planned for this study.

7.4 Analysis of the Study

All statistical tests will be two-sided and a difference resulting in a p-value of less than or equal to 0.05 will be considered statistically significant. All p-values will be rounded to and displayed in four decimals. If a p-value less than 0.0001 occurs it will be shown in tables as <0.0001.

There will be no multiplicity adjustments.

Descriptive summaries of variables will be provided where appropriate. For continuous variables, the number of non-missing values (n) and the median, mean, standard deviation, minimum, and maximum will be tabulated by dosage group. For categorical variables, the counts and proportions of each value will be tabulated by dosage group. Since this study allows for subjects to change their dose level during additional treatment visits after Day 43, the dose level can change over the course of the study; see Section 8 for how summaries by dosage group will be handled when dose levels vary.

Expansion of descriptive table categories within each treatment may occur if such elaborations are thought to be useful.

Assessments completed during the 6-month follow up period after study treatment will not appear in any tables or graphs (unless noted otherwise), but will be included in the data listings, classified under the last dose level the subject took at the last treatment visit prior to the end of study.

All collected data will be presented in listings. Data not subject to analysis according to this plan will not appear in any tables or graphs but will be included in the data listings.

Post-hoc exploratory analyses not identified in this SAP may be performed to further examine the study data. These analyses will be clearly identified as such in the final clinical study report.

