sample will not be entered into the treatment phase as they are not deemed suitable candidates for the HAAH vaccine. The 21-day treatment phase will allow the patient sufficient time to recover from any adverse effects of the vaccine before the next dose. It is anticipated that the SNS-301 will lead to the development of active anti-HAAH immunity with consistent polyclonal anti-HAAH antibody titers in addition to development of anti-HAAH T-cells. This is further supported by our current data from patients treated up to now. Based on this, a decision has been made to limit the total number of injections to 9, which accounts for 6 months of treatment with an additional 6 months of follow up, with monthly measurement of PSA levels and anti-HAAH immunity parameters. Patients who, at the time of this amendment, have received more than 9 injections, will cease treatment at the time of their last injection when this amendment goes into effect and will also be followed for 6 months, as will patients whose disease progression leads to treatment stoppage before 1 year. Patients with evidence of progression and declining HAAH immune parameters have the option of resuming therapy on the study protocol in the 6 month follow up period. All patients are eligible for enrollment in the expanded access protocol after study closure.

4. Study Objectives and Endpoints

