7.4.5 Derived Variables

- Non Treatment Emergent Adverse Events include all AEs that stopped the day prior to the first vaccination, started prior to the first vaccination but did not increase in severity or relationship during treatment, or started more than 30 days after *the final study treatment administration* date.
- Treatment Emergent Adverse Events (TEAEs) include all AEs that start on or after the first study treatment administration, or AEs that are present prior to the first administration, but their severity or relationship increases after the first administration up to and including 30 days after the final administration date.
- Change from baseline will be calculated as the observed value at the current visit or time point minus the observed value at baseline.
- Number of doses administered will be calculated for each subject by summing the number of doses administered over all visits.
- *Prior medications* include all medications that have a start date prior to the date of first study treatment administration.
- Concomitant medications include all medications that are taken on or after the date of first study treatment administration.
- The end of treatment phase visit will be the visit immediately after the last visit where treatment was administered. This visit will be the first follow up visit for subjects who have any follow up visits, or the End of Study visit for all other subjects.

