7.4.7 Handling of Early Termination Visits and Additional Treatments

Early termination visit data (on or prior to Day 43) for safety variables will be analyzed at the closest scheduled visit. If the closest visit has valid data, the early termination data will be assigned to the next available visit.

Any safety or immunologic data collected for additional treatments (after Day 43) will be summarized as visits separate from the scheduled visits (up to and including Day 43 and End of Study).

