8.7 Immunological Analysis

All immunological analyses will be conducted on the Immunologic Population.

As for the safety variables, subjects will be summarized through Day 43 using the assigned dose level as the dosage group. For additional treatment visits and end of treatment phase visit, subjects will be summarized by cohort and by the dose level the subject took at the visit immediately prior to the current visit—this allows for subjects who changed their dose level to be summarized at the new (elevated) dose level.

The variables that will be analyzed are listed in Table 8-1:

Туре	Name	Unit
Antigan analifia anti IIA All antihadu titara	ΗΑΑΗ-1λ	Antibody Units / mL
Antigen-specific anti-HAAH antibody titers	H460 (HAAH)	Antibody Units / mL
	CD4+ T Cells IFN-γ	% of CD4+ T cells
Cellular Immune Response	CD8+ T Cells IFN-γ	% of CD8+ T cells
	HAAH-Specific B Cells	% of B cells
	B Cells	% of Leukocytes
	T Cells	% of Leukocytes
	CD4+ T Cells	% of T cells
	CD8+ T Cells	% of T cells
Immunophenotyping	CD3+, CD56+ Cells	% of Leukocytes
1 51 6	NK Cells	% of Leukocytes
	Neutrophils	% of Leukocytes
	Eosinophils	% of Leukocytes
	Monocytes	% of Leukocytes

 Table 8-1.
 Variables Included in Immunological Analysis

Assay data will be tabulated by time point, An appropriate data transformation (e.g., log_{10} transformation) may be applied to better satisfy assumptions of symmetry and homoscedasticity (constant variance). Graphical representations of the longitudinal immune responses will also be given.

All data related to immunologic collection and analysis will be listed.

9 References

10 Appendices

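### The SAP keeps geometric mean titer by dose and duration of anti-HAAH titers as secondary endpoints, but its stated analysis rules leave most off-treatment titers in listings and specify neither a duration measure nor a GMT calculation.

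*SAP*

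**What the plan says.** **Endpoints.** SAP 6.4 lists "Geometric mean titers of anti-HAAH antibodies by dose" among the secondary endpoints. Under the pharmacodynamic ones it lists "Duration of antigen-specific anti-HAAH antibody titers" and "Correlation of anti-HAAH titers and serum HAAH levels".

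**Data collected.** Protocol 3.4 describes six months of follow-up after treatment "with monthly measurement of PSA levels and anti-HAAH immunity parameters". Protocol 5.5.2.7 and SAP Table 4-1 schedule immunologic blood at the follow-up visits, which fall every 28 ± 3 days.

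**Visits summarised.** SAP 7.4 sets the default: "Assessments completed during the 6-month follow up period after study treatment will not appear in any tables or graphs (unless noted otherwise". SAP 8.7 summarises titers through Day 43 and then adds: "For additional treatment visits and end of treatment phase visit, subjects will be summarized by cohort and by the dose level". SAP 7.4.5 defines the end of treatment phase visit: "This visit will be the first follow up visit for subjects who have any follow up visits". SAP 7.4.7 says that safety or immunologic data from additional treatments "will be summarized as visits separate from the scheduled visits (up to and including Day 43 and End of Study", which mentions End of Study as a scheduled visit in passing. For PSA, by contrast, SAP 8.5 expressly names follow-up visits and end of study.

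**Statistics.** SAP 7.4 gives n, median, mean, SD, minimum and maximum for continuous variables. The titer figures in SAP 10.1 are titled Mean (SD). SAP 8.7 permits a transformation such as log10 but does not require one. GMT appears in SAP section 4 (design overview) and in 6.4, but not as a calculation in sections 7 or 8 or in the output list. The table shells are in a separate document that was not available.

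**The concern.** How long antibody persists after dosing stops can be learned only from the off-treatment samples, and the default rule removes most of these from the summaries. No derived variable, threshold, start, end or censoring rule for duration appears in SAP 7.4.5 or 8.7, and no duration output is listed in 10.1.

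The GMT endpoint has a similar gap. A programmer following sections 7 and 8 would produce an arithmetic mean and SD for an endpoint defined as a geometric mean. Titers from serial dilution are usually right-skewed, so the two can differ a good deal, and in small cohorts an SD bar may run below zero.

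Immunogenicity is in the trial title and in the SAP's secondary objective. If the GMT and duration summaries are not specified now, they would have to be added later under the post-hoc provision of SAP 7.4, with any threshold chosen after the data are seen. That matters more because patients with progression and declining immune parameters may resume SNS-301 during follow-up. Off-treatment titers are therefore observed selectively.

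**Working it through.** The plan gives no figure on this point to reproduce. The check has two parts.

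**1. Share of off-treatment titer visits left in listings**

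Inputs: six months of follow-up, about 182.6 days (365.25/2), with visits every 28 ± 3 days (SAP Table 4-1). Resumed dosing is ignored.

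- At 28 days: 182.6/28 = 6.5, so 6 complete visits. At 31 days: 5.9, so 5. At 25 days: 7.3, so 7.
- If 8.7 admits only the first follow-up visit, the listing-only share is (v − 1)/v: 5/6 = 83% (4/5 = 80% to 6/7 = 86%).
- If 7.4.7 also admits a separate final End of Study visit, it is (v − 2)/v: 4/6 = 67% (3/5 = 60% to 5/7 = 71%).

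Most off-treatment titer visits are listing-only on either reading.

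End of Study is itself unclear. SAP section 4 places it 28 days after the last dose, which would make it the first follow-up visit. SAP 7.4.5 and 8.5 treat it as distinct from the end of treatment phase visit when a subject has follow-up visits.

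**2. Arithmetic mean against GMT**

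The documents give no titer SD, so the log10 SD *s* is an assumption, taken over 0.2 to 0.8. For lognormal titers the population ratio of arithmetic to geometric mean is exp[(s·ln 10)²/2]. At s = 0.5 this is exp[(1.151)²/2] = exp(0.663) = 1.94. Small cohorts show a smaller typical ratio, so 400,000 cohorts were simulated per cell:

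| n | s | Median ratio | Share with ratio ≥ 1.5 |
|---|---|---|---|
| 3 | 0.2 | 1.05 | 0.2% |
| 3 | 0.5 | 1.32 | 36% |
| 3 | 0.8 | 1.91 | 67% |
| 6 | 0.2 | 1.08 | <0.1% |
| 6 | 0.5 | 1.55 | 54% |
| 6 | 0.8 | 2.71 | 90% |

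At s = 0.5 the SD exceeds the mean in 30% of cohorts of 3 and 43% of cohorts of 6, so the lower error bar in a Mean (SD) figure would be negative.

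The tabulated median helps in part. Its ratio to the cohort's GMT has a median of 1.00 to 1.11 across these cells. At s = 0.5, however, it still differs by 1.5-fold or more in 28% (n=3) and 13% (n=6) of cohorts.

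**The case against.** The strongest reply is that SAP 8.7 also promises tabulation of assay data by time point and graphs of the longitudinal immune responses, without a visit limit. These could be read as the exception that 7.4 allows. It is the weaker reading: 8.7 names its own post-Day 43 visits and leaves out follow-up, whereas 8.5 writes follow-up in. The general sentences do not clearly override that.

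Other replies stand in part. The protocol promises only descriptive display by cohort, all immunologic data are listed, medians are tabulated, and listings for about 18 patients can be read. A log10 transformation is allowed, and the unseen shells may contain a GMT row. These limit the severity; they do not put the endpoint calculations into the SAP.

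Some stronger readings are tempting but unsupported:

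- *The SAP never mentions GMT.* It does, in sections 4 and 6.4. What is missing is the calculation.
- *The output list proves that PSA follow-up is tabulated and titer follow-up is not.* The PSA table through End of Study holds velocity and doubling time. The by-visit PSA table has the same form of title as the titer table. Only the text of 8.5 against 8.7 carries the contrast.
- *Serum HAAH is only a positive or negative test, so the correlation cannot be done.* SAP 6.4 refers to serum HAAH levels, and 7.4.2 lists serum HAAH results as sponsor-supplied. HAAH assessment is, however, scheduled only at screening, so feasibility is unknown.
- *The dose decision is compromised.* Protocol 6.1 mentions immunogenicity in the primary safety analysis, and the synopsis lets PD data alter the RP2D. Neither says how these two summaries would enter, and SAP 6.3 places the primary endpoints outside its scope.

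**Conclusion.** The point holds as a gap in secondary-endpoint reporting that should be closed.

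On duration, confidence is high. The measure is undefined, and 4 or 5 of 6 off-treatment titer visits per patient are listing-only (60% to 86% for 5 to 7 visits), assuming 28-day visits, full follow-up and no resumed dosing.

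On GMT, it is clear that sections 7 and 8 and the output list specify no calculation. The consequence is less certain. The typical arithmetic-to-geometric ratio runs from about 1.05 to 1.9 at n=3 and 1.08 to 2.7 at n=6, that is, from negligible to large. It depends on an assumed log10 SD of 0.2 to 0.8 and lognormal titers, and a GMT row in the shells cannot be excluded.

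A reader might infer that the off-treatment titers are lost. They are not: they remain in the listings.

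Two lesser omissions belong with this point. Table 8-1 includes CD8+ IFN-γ but not the percent specific lysis described in protocol 5.5.3.2. The titer against serum HAAH correlation has no variable, method or output. SAP 7.4.1 nevertheless declares the analyses consistent with the protocol.

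**What to change.** In SAP 8.7:

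(a) **Follow-up and duration.** Add the follow-up and End of Study visits to the anti-HAAH tables and figures as an express exception to 7.4, by time since last dose and under the last dose level. Show titers after resumed SNS-301 separately, with the number resumed. Add a descriptive duration summary, for example time from last dose to the first titer below 4 times baseline, censored at the last titer or at resumption. Give the number at or above that threshold at each visit with its denominator. The threshold serves the analysis only. State that subjects not resumed are a selected group, since resumption is tied to declining immune parameters.

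(b) **GMT.** Analyse titers on the log10 scale. Report GMT by dose with a geometric measure of spread, in tables and figures, in place of Mean (SD). Keep n, median and range, and state a rule for titers below the detection limit.

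(c) **Lesser items.** Declare in 7.4.1 that percent specific lysis and the titer against serum HAAH correlation are not analysed, or add them if the data exist. Reconcile the End of Study visit between SAP sections 4, 7.4.5 and 7.4.7.

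**Cost.** SAP wording and a few more outputs; (a) and (b) use samples already scheduled. Estimates will be very imprecise. The 95% CI factor is 10^(t·s/√n), which at an assumed s = 0.5 is 10^(4.303 × 0.5/√3) = 17.5 either way at n=3 and 10^(2.571 × 0.5/√6) = 3.3 at n=6. The results should be read descriptively.
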